#### 10.1.1. Screening Period

The Screening Period begins at the time of consent of the study subject. The Investigator will conduct the following assessments:

- Review of inclusion and exclusion criteria
- Review and record medical history and concomitant medications
- Conduct an assessment for IRC; if an IRC is suspected, then the physical examination will confirm the actual presence/absence of the IRC. If an IRC is present, the subject meets exclusion criteria 6 and is ineligible for the study.
- Measure oral body temperature
- Conduct a RAT or Food and Drug Administration (FDA)-approved PCR test for influenza A and B on an adequate nasal specimen, in accordance with the manufacturer's instructions. The subject must have a positive RAT result and/or a Food and Drug Administration (FDA) approved PCR test and at least one clinical sign or symptom consistent with influenza (see 2b below).

**OR** have clinical signs and symptoms consistent with acute influenza infection consisting of an oral temperature  $\geq 100^{\circ}\text{F}$  ( $37.8^{\circ}\text{C}$ ) with at least one respiratory symptom of at least moderate severity (cough or rhinitis) and at least one constitutional symptom of at least moderate severity (myalgia [aches and pains], headache, feverishness, or fatigue) (See Section 8.1). **Note: Enrollment at each site by clinical symptoms alone will be approved by the Sponsor at the beginning of each influenza season once influenza has been confirmed in the local community. The Sponsor may withdraw approval for symptomatic screening in any season based upon trends in influenza surveillance data. Prior to Sponsor approval or after approval is withdrawn, Criteria 2 must be met by a positive influenza RAT test and/or PCR. During the period of approval, clinical symptoms alone will be adequate to meet Criteria 2.**

The subject must have at least 1 respiratory symptom (cough, sore throat or nasal symptoms) of at least moderate severity, in addition to at least 1 constitutional symptom (myalgia, headache, feverishness, or fatigue) of at least moderate severity to be eligible for the study

- Measure vital signs (blood pressure, pulse rate, and respiration rate)
- Perform a complete physical examination. Examination of the breast and urogenital system may be omitted as per the institution's/Investigator's clinical routine.

- Perform a urine or serum pregnancy test (non-pregnant females of childbearing potential only)

Eligible subjects will be enrolled. The study pharmacist/designee will prepare an order for study drug as defined in Section 9.3 , which includes the subject's study number.

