**Criteria for inclusion:**

Subjects must meet the following criteria to be eligible for study participation:

1. Male and female subjects age  $\geq 18$  years.
2. The subject must meet one of the following two criteria:
  - a. A positive influenza Rapid Antigen Test (RAT) and/or a Food and Drug Administration (FDA)-approved polymerase chain reaction (PCR) test and at least one clinical sign or symptom consistent with influenza (see 2b below).

**OR**

- b. Clinical signs and symptoms consistent with acute influenza infection consisting of an oral temperature  $\geq 100^{\circ}\text{F}$  ( $37.8^{\circ}\text{C}$ ) with at least one respiratory symptom of at least moderate severity (cough or rhinitis) and at least one constitutional symptom of at least moderate severity (myalgia [aches and pains], headache, feverishness, or fatigue). **Note: Enrollment at each site by clinical symptoms alone will be approved by the Sponsor at the beginning of each influenza season once influenza has been confirmed in the local community. The Sponsor may withdraw approval for symptomatic screening for any season based upon trends in influenza surveillance data. Prior to Sponsor approval or after approval is withdrawn, Criteria 2 must be met by a positive influenza RAT test and/or PCR. During the period of approval, clinical symptoms alone will be adequate to meet Criteria 2.**
3. Onset of symptoms no more than 48 hours before presentation for screening. However, due to historically delayed presentation for medical care in the adult population, approximately 20% of the elderly population may be enrolled with symptoms starting  $> 48$ -hours but  $\leq 72$ -hours prior to presentation for screening. Note: Time of onset of illness is defined as either (1) the time when the temperature (either oral or rectal) was first measured as elevated (at least one  $^{\circ}\text{C}$  of elevated temperature), OR (2) the time when the subject experienced the presence of at least one respiratory symptom AND the presence of at least one constitutional symptom together.
4. Either age  $\geq 65$  years AND/ OR presence of one of the following risk factors:
- Pregnancy, including women who are up to 2 weeks post-partum
  - Resident of a nursing home or long-term care facility
  - History of chronic lung disease including obstructive pulmonary disease (COPD), persistent asthma or cystic fibrosis

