### 8.1. Subject Inclusion Criteria

1. Male and female subjects age  $\geq$  18 years.
2. The subject must meet one of the following two criteria:
  - a. A positive influenza Rapid Antigen Test (RAT) and/or a FDA-approved PCR test and at least one clinical sign or symptom consistent with acute influenza infection as listed in 2b below.

**OR**

- b. Clinical signs and symptoms consistent with acute influenza infection consisting of an oral temperature  $\geq$  100°F (37.8°C) with at least one respiratory symptom of at least moderate severity (cough or rhinitis) and at least one constitutional symptom of at least moderate severity (myalgia [aches and pains], headache, feverishness, or fatigue). **Note: Enrollment at each site by clinical symptoms alone will be approved by the Sponsor at the beginning of each influenza season once influenza has been confirmed in the local community. The Sponsor may withdraw approval for symptomatic screening in any season based upon trends in influenza surveillance data. Prior to Sponsor approval or after approval is withdrawn, Criteria 2 must be met by a positive influenza RAT test and/or PCR. During the period of approval, clinical symptoms alone will be adequate to meet Criteria 2.**
3. Onset of symptoms no more than 48 hours before presentation for screening. However, due to historically delayed presentation for medical care in the adult population, approximately 20% of the elderly population may be enrolled with symptoms starting  $>$  48-hours but  $\leq$  72-hours prior to presentation for screening. Note: Time of onset of illness is defined as either (1) the time when the temperature (either oral or rectal) was first measured as elevated (at least one °C of elevated temperature), OR (2) the time when the subject experienced the presence of at least one respiratory symptom AND the presence of at least one constitutional symptom together.
4. Either age  $\geq$  65 years AND/ OR presence of one of the following risk factors:
  - a. Pregnancy, including women who are up to 2 weeks postpartum
  - b. Resident of a nursing home or long-term care facility
  - c. History of chronic lung disease including obstructive pulmonary disease (COPD), persistent asthma or cystic fibrosis
  - d. History of heart disease including myocardial infarction, angina requiring treatment, congestive heart failure requiring treatment, arrhythmia including atrial fibrillation and valvular dysfunction

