1.1. STUDY OVERVIEW

Protocol BCX1812-306 is a multicenter, single-arm, open-label study to evaluate the safety, PK, and effectiveness of a single dose of peramivir administered intravenously (IV) in elderly subjects (≥ 65 years of age) with acute uncomplicated influenza and in younger subjects (< 65 years of age) with acute uncomplicated influenza who are at higher risk for influenza complications. Elderly subjects will not be classified as high or low risk and will be captured as elderly only.

Approximately 120 subjects will be enrolled in this open-label study (a minimum of 80 elderly subjects will be enrolled). A subject's duration of participation in this study is expected to be 14 days and will include up to 4 clinic visits. It is expected that most subjects will have the Screening visit and the Day 1 Treatment visit on the same day. Following treatment on study Day 1, subjects will undergo follow-up assessments on Days 3, 7, and 14 in the clinic. Subjects will be discharged from this study on Day 14. Additional unscheduled visits may be required for subjects who report symptoms of influenza of moderate or severe intensity at Day 14 or have persistent adverse events (AEs) and/or treatment-emergent laboratory findings that require medical monitoring or management.

Eligible subjects will have a positive influenza Rapid Antigen Test (RAT) and/or a Food and Drug Administration (FDA) approved polymerase chain reaction (PCR) test and at least one clinical sign or symptom consistent with influenza OR clinical signs and symptoms consistent with acute influenza infection consisting of an oral temperature $\geq 37.8^{\circ}\text{C}$ / 100°F with at least one respiratory symptom of at least moderate severity (cough or rhinitis) and at least one constitutional symptom of at least moderate severity (myalgia, headache, feverishness, or fatigue).

Subjects will receive a single IV dose of 600 mg peramivir (or less if renally impaired), which will occur over 15 to 30 minutes.

An adequate nasal swab specimen will be collected from all enrolled subjects at Baseline (predose) for virus subtype identification and quantitative virologic assessments and at the follow-up assessments on study Days 3, 7, and 14.

Specimens obtained from all subjects on Day 1 and the last specimen that yields influenza virus on culture will also be assessed for susceptibility to neuraminidase inhibitors. A central laboratory will perform all virologic assessments.

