The ability to perform usual activities is defined as a subject rating of 10 (able to perform all usual activities fully) on the visual analog scale the subject uses to rate his or her current ability to perform usual activities compared with normal ability.

Time to Event

Time to a given event is defined as the number of hours (days) from initiation of earliest study treatment until the event occurs. The unit of measurement will vary based upon the endpoint and its respective schedule of assessment.

Time to Alleviation of Symptoms

Time to Alleviation of Symptoms is the number of hours from initiation of study drug to start of the 21.5 hour period (24 hours less 10%) where all symptoms of influenza are recorded as none or mild.

Change from Baseline

Change from baseline for a given endpoint is defined as the Study Day X value minus the Baseline Value.

Adverse Event (AE)

According to the protocol, an AE is any untoward medical occurrence in a clinical study subject. No causal relationship with the study drug or with the clinical study itself is implied. An AE may be an unfavorable and unintended sign, symptom, syndrome, or illness that develops or worsens during the clinical study. Clinically relevant abnormal results of diagnostic procedures including abnormal laboratory findings (eg, requiring unscheduled diagnostic procedures or treatment measures, or resulting in withdrawal from the study) are considered to be AEs.

AEs may be designated as “nonserious” or “serious” (see Protocol Section 11.1.1.1). Surgical procedures are not AEs but may constitute therapeutic measures for conditions that require surgery. The condition for which the surgery is required is an AE if it occurs or is detected during the study period. Planned surgical measures permitted by the clinical study protocol and the condition(s) leading to these measures are not AEs if the condition(s) was (were) known before the start of study treatment. In the latter case the condition should be reported as medical history.

Assessment of symptoms of influenza will be documented in a Subject Diary and analyzed as a measure of effectiveness of the study treatment. These symptoms will not be reported as AEs unless the symptom(s) worsen to the extent that the outcome fulfills the definition of a serious adverse event (SAE), which then must be recorded as such (see Protocol Section 11.1.1.2).

All AEs will be recorded on the ADVERSE EVENTS CRF.

Treatment-emergent Adverse Events (TEAEs)

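### Protocol 10.1.1 adds a moderate respiratory-plus-constitutional symptom pair that criterion 2a does not ask for, so some test-positive subjects are eligible under one text and deviations under another

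*Protocol*

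**What the plan says.** Protocol 8.1 makes the two routes of criterion 2 alternatives: "The subject must meet one of the following two criteria". Route 2a is a positive rapid antigen or PCR test plus "at least one clinical sign or symptom consistent with acute influenza infection as listed in 2b below". The Synopsis has the same route: "and at least one clinical sign or symptom consistent with influenza (see 2b below"). Route 2b, usable only while the sponsor has approved symptom-only enrolment at the site, needs an oral temperature of at least 100°F "with at least one respiratory symptom of at least moderate severity (cough or rhinitis") and a constitutional symptom of at least moderate severity. SAP 1.1 repeats the either/or structure: "at least one clinical sign or symptom consistent with influenza OR clinical signs and symptoms".

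Protocol 10.1.1 restates 2a, then 2b, then the note on sponsor approval. A separate paragraph follows: "The subject must have at least 1 respiratory symptom (cough, sore throat or nasal symptoms") of at least moderate severity, in addition to a constitutional symptom of at least moderate severity. The paragraph presents this as a condition of eligibility and makes no exception for test-positive subjects. No inclusion criterion contains it, and neither does the SAP. The opening of Protocol Section 8 ties eligibility to the listed inclusion and exclusion criteria.

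On the analysis side, SAP 3.3.8 times alleviation from study drug to the start of the 21.5-hour period "where all symptoms of influenza are recorded as none or mild". The ITTI population (SAP 4.2) requires enrolment, treatment and PCR confirmation, with no condition on symptom severity before dosing.

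**The concern.** Two operative texts define different study populations. A test-positive subject without the moderate pair can be enrolled correctly under 8.1 and be a protocol deviation under 10.1.1. Sites may enrol differently, and the eligibility summary and deviation listing planned in the SAP would depend on which rule the coder applied.

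There is also a possible effect on an effectiveness endpoint. A subject whose seven symptoms are all scored 0 or 1 at dosing, and stay there, satisfies the alleviation definition at or near time zero. The 10.1.1 paragraph would keep that subject out. Under 2a the subject may come in, and no SAP rule then stops the near-zero time from entering the Kaplan-Meier estimate.

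**Working it through.** The plan gives no figure on this point, so the check is a comparison of conditions.

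**Rule A** (Synopsis, 8.1, SAP 1.1): [positive test AND at least one sign or symptom] OR [temperature ≥ 100°F AND moderate cough or rhinitis AND a moderate constitutional symptom].

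**Rule B** (10.1.1 read to its end): Rule A AND [moderate cough, sore throat or nasal symptom] AND [moderate constitutional symptom].

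*Route 2b.* Taking rhinitis as a nasal symptom, everyone who meets 2b already meets the added condition. It changes nothing there.

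*Route 2a.* Test-positive subjects who meet all other criteria:

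| Presentation | Rule A | Rule B | All symptoms 0 or 1 at dosing? |
|---|---|---|---|
| Moderate respiratory and moderate constitutional symptom | eligible | eligible | no |
| Moderate cough or rhinitis, no moderate constitutional symptom | eligible | not eligible | no |
| Moderate constitutional symptom, no moderate respiratory symptom | eligible | not eligible | no |
| Temperature ≥ 100°F, every symptom none or mild | eligible | not eligible | yes |
| Lower temperature, mild symptoms only | depends on whether 2a takes over the severity in 2b | not eligible | yes |

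The rules disagree in rows two to four whichever way 2a is read, and in row five if 2a accepts mild symptoms. Only rows four and five bear on time to alleviation.

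*Symptom lists.* 2b names cough or rhinitis; 10.1.1 names cough, sore throat or nasal symptoms. A febrile subject with moderate sore throat and moderate headache but no cough or rhinitis fails 2b, yet meets the 10.1.1 paragraph.

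*Illustration only.* The documents give neither the share of ITTI subjects at none or mild at dosing nor a median for the others. Assume a share p who are counted as alleviated at time zero, and an exponential time with median 80 h for the rest. The overall median solves (1 − p) × 2^(−t/80) = 0.5, so t = 80 × log2[2(1 − p)].

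- p = 0: 80 h
- p = 0.10: 80 × log2(1.8) = 80 × 0.848 = 67.8 h
- p = 0.20: 80 × log2(1.6) = 80 × 0.678 = 54.2 h

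For a given share at none or mild at dosing, this is the largest shift under these assumptions. It requires all of those subjects to stay at none or mild for the first 21.5 hours.

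**The case against.** The kindest reading is that the extra paragraph merely elaborates 2b. The text does not bear this out. On 2b the paragraph would be redundant, and it would misstate 2b by dropping the temperature and changing the respiratory list.

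A better objection is that one paragraph in a procedures list stands against the Synopsis, 8.1, the opening of Section 8 and SAP 1.1, and may be leftover wording. That is plausible. But the documents state no order of precedence between 10.1.1 and 8.1. The clause in SAP 5.4 that lets the SAP override the protocol sits in an analysis document and does not tell a site whom to enrol.

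Three further points stand:

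- A reader might infer that 2a admits symptoms of any severity. Section 8.1 refers to symptoms as 2b lists them, and 2b lists them at moderate severity or worse, so 2a may take over that severity. The any-severity reading is possible but not established. The conflict survives either way, because 2a asks for one sign or symptom and 10.1.1 asks for a pair.
- A reader might infer that eligibility turns on which page a site consults. The conflict is also internal to 10.1.1, which states 2a shortly before the paragraph that overrides it.
- Subjects with one moderate symptom of either kind are not at none or mild at dosing. Subjects who present within 48 hours of onset may also worsen after dosing. The near-zero event times therefore come from only part of the disputed group.

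The SAP will also summarise the Baseline Composite Symptom Score for the ITTI population, which gives some view of severity at entry. It does not change how time to alleviation is computed.

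**Conclusion.** The contradiction is real and rests on the text alone. It affects test-positive subjects without a moderate respiratory and a moderate constitutional symptom, and decides whether they are eligible or deviations.

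The consequence for time to alleviation is narrower but does not vanish. Even if 2a requires moderate severity, a subject who qualifies by test and temperature alone can be at none or mild at dosing and count as alleviated almost at once.

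A reader might take 67.8 h or 54.2 h as the size of the bias, or conclude that differences between sites pass straight into the effectiveness estimate. The documents support neither. The shares, the 80 h median and the exponential form are all assumed, and the calculation shows what admitting mild subjects could do, not what the inconsistent wording does.

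The weight is moderate: safety is the primary endpoint, no hypothesis is tested, and time to alleviation is a descriptive secondary summary. In a single-arm study, though, that summary can be interpreted only if the enrolled population is clearly defined. Nothing here shows which eligibility rule is the right one.

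**What to change.** 1. Reconcile the Synopsis, Protocol 8.1, Protocol 10.1.1 and SAP 1.1 to one eligibility rule. The 10.1.1 paragraph can be removed, limited to 2b (where it would be redundant), or carried into criterion 2a. The sponsor should say which was intended.
2. State whether 2a requires moderate severity, and use one respiratory symptom list throughout.
3. If the reconciled rule still admits subjects with no symptom scored 2 or 3 before dosing, add a sentence to SAP 5.2.2: time to alleviation is presented in ITTI subjects with at least one such pre-dose score, with the number excluded reported. Name the score used, since Protocol Table 1 has study personnel record symptoms at Screening while the SAP baseline score comes from a pre-dose diary entry.

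The cost is a wording correction, one SAP sentence and a slightly smaller analysis set for one endpoint; the plan already calls for pre-dose scores. The Synopsis estimates the last subject's completion in April 2018 and the SAP carries the date 14 June 2018. If enrolment has closed, item 1 becomes a statement of which rule governs deviation coding, and item 3 can still be made.

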#### **10.1.2. Treatment Period**

Randomization and study drug administration should begin as soon as possible following determination that the subject is eligible for enrollment at Screening. Therefore, it is anticipated that the date of Screening and Day 1 (date of administration of the first dose of study medication) will be the same day. Day 1 represents the first day of dosing.

##### **10.1.2.1. Baseline (Pre-dose)/Day 1**

The following Baseline procedures/evaluations will be performed after Screening and prior to dosing on Day 1:

- Obtain a bilateral adequate nasal swab specimen for viral subtyping, culture, quantitative PCR assay and susceptibility to neuraminidase inhibitors.
- Obtain and record body temperature
- Blood and urine specimen collection for clinical chemistry and clinical hematology tests as specified in Sections 11.2.1 and 11.2.2 and a serum sample for future influenza antibody analysis.

Following completion of the baseline procedures administer study drug:

- Administer study drug (at hour 0) and record the calendar date and 24-hour clock time for the start and finish of the IV infusion.
- Obtain and record body temperature

##### **10.1.2.2. Day 1/Post-dose**

The following procedures/evaluations will be performed post-dose on Day 1:

- Collect up to 3 plasma samples, where possible, during the following time periods, beginning from the end of dosing until release from the site. For each plasma sample the calendar date and 24-hour clock time of sample collection will be recorded:
  - One time point immediately following completion of the infusion
  - One time point from 30 minutes to 1 hour post-infusion
  - One time point from 1 hour to 3 hours post-infusion
- Train the subject/caregiver on the recording of the following in the subject diary:
  - Subject's body temperature, obtained at approximately 12-hour intervals each day until the temperature normalizes for 48 hours (and 4 hours from last antipyretic medication administration or immediately prior to administration).

- Instruct the subject to assess his/her time lost from work, if applicable, and the recording of the subject's ability to perform usual daily activities using a 0 to 10 visual analogue scale.
- Assessment of signs and symptoms of influenza twice daily beginning on Day 1 (see Section [10.2.2](#)).
- Review and record concomitant medications
- Obtain and record body temperature
- Review and record AEs

